13.2. APPENDIX: DRUGS POTENTIALLY AFFECTING MUSCLE FUNCTION

List of drug(s) or supplements that potentially may affect muscle function includes, but is not limited to, the following:

1. Statins
2. Steroids
3. Testosterone or other growth hormone agonists
4. Beta-agonists
5. Creatine
6. Colchicine
7. Benzylpenicillin

## List of Abbreviations

AE	adverse event
AESI	adverse event of special interest
ATC	Anatomical Therapeutic Chemical
BID	twice daily
BLQ	below the limit of quantitation
BMI	body mass index
CI	confidence interval
COA	clinical outcome assessment
COVID-19	coronavirus disease 2019
CRF	case report form
ECG	electrocardiogram
FSHD	facioscapulohumeral muscular dystrophy
FSHD1	facioscapulohumeral muscular dystrophy type 1
FSHD-HI	FSHD Health Index
LMV	lean muscle volume
LS	least-squares
MedDRA	Medical Dictionary for Regulatory Activities
MFF	muscle fat fraction
MFI	muscle fat infiltration
MFM	Motor Function Measure
MRI	Magnetic Resonance Imaging
MSK	musculoskeletal
OLE	open-label extension
PGIC	Patient's Global Impression of Change
PO	orally
PT	preferred term
RWS	Reachable Workspace
RSA	relative surface area
SAE	serious adverse event
SAP	statistical analysis plan
SAS	Statistical Analysis Software
SD	standard deviation
SE	standard error
SOC	system organ class
TEAE	treatment-emergent adverse events
TUG	Timed Up and Go
WHODD	World Health Organization drug dictionary

## 1. Introduction

This statistical analysis plan (SAP) describes the analyses and data presentation for the Open-label extension (OLE) part of protocol FIS-002-2019 which is being conducted under the sponsorship of Fulcrum Therapeutics (Fulcrum) in accordance with applicable standard operating procedures. The efficacy analyses will be conducted at OLE visits with available subject data. Statistical analyses are being conducted under contract with █, part of Thermo Fisher Scientific, in collaboration with Fulcrum.

The Clinical, Data Management, and Biostatistics departments at █ will work diligently and collaboratively with Fulcrum to ensure that the data collected and analyzed for this study are of high quality. This will be accomplished in part by having thorough edit checks written, programmed, and updated as needed.

This SAP is based on the protocols version 4.0 (COVID-19 Pandemic Emergency Amendment) dated 10Apr2020 and version 5.0 dated 16Aug2022. This SAP contains definitions of analysis population, derived variables, and statistical methods for the analysis of the OLE and in some parts of this SAP, a combination of placebo-controlled treatment period and OLE analysis. A separate SAP was created for the placebo-controlled treatment period.

The OLE will evaluate the safety, tolerability, and efficacy of long-term dosing with losmapimod in treating subjects with Facioscapulohumeral Muscular Dystrophy type 1 (FSHD1).

The term study drug that is being used throughout this document refers to losmapimod and/or placebo.

## **2. Objectives for OLE**

### **2.1. Primary Objectives**

The primary objective of the OLE is to evaluate the safety and tolerability of long-term dosing of losmapimod in FSHD1 subjects, based on protocol versions 4.0 and 5.0.

### **2.2. Secondary Objectives**

The secondary objectives of the OLE are as follows:

- To evaluate the changes from baseline in MFF, LMV, and MFI in FSHD1 subjects, as measured by MSK MRI, based on protocol version 4.0.
- To evaluate the plasma concentrations of losmapimod in FSHD1 subjects, based on protocol versions 4.0 and 5.0.

### **2.3. Exploratory Objectives**

The exploratory objectives of the OLE, based on protocol version 4.0, are as follows:

- To evaluate the changes from baseline in the following COAs:
  - RWS with and without weights
  - Classic and FSHD TUG
  - Muscle strength by hand-held quantitative dynamometry
  - MFM Domain I
  - FSHD-HI
  - PGIC
- To evaluate the changes from baseline in inflammatory, immune, apoptotic, and other muscle disease transcripts in circulating proteins in plasma and serum.

### **3. Investigational Plan**

#### **3.1. Overall Study Design and Plan**

Once subjects reach Week 48, they will have the option to roll over into the OLE, with all subjects receiving 15 mg PO losmapimod tablets BID. Subjects who wish to roll over into the OLE must complete all procedures from the Week 48 end of placebo-controlled treatment period/start of OLE visit.

Subjects will remain in the OLE until study drug approval or until the study is discontinued by the sponsor. All subjects who complete or discontinue from treatment will complete a safety follow-up visit 7 days (+/- 3 days) after the last dose of study drug.

During the OLE, subjects will attend clinic visits approximately every 12 weeks. Study drug (open-label losmapimod) will be administered BID and should be taken with food. The first dose of OLE drug will be the day after the Week 48 visit.

The OLE will evaluate the safety and tolerability of long-term dosing with losmapimod in treating subjects with FSHD1. The efficacy data will be collected until protocol version 5.0 is executed. The efficacy analysis will be conducted when available efficacy data are fully cleaned.

Prior to the COVID-19 pandemic, subjects who reached the Week 24 visit had the option to roll over into the OLE. Subjects who had already rolled over to the OLE prior to the COVID-19 pandemic will remain on open label treatment. Their next clinic visits will follow the assessments for the Week 36 and Week 48 visits in the placebo-controlled portion of the study as described in the COVID-19 Pandemic Emergency protocol version 4.0. The first dose of OLE drug for these subjects will be the day after the Week 24 visit.

#### **3.2. Study Endpoints**

##### **3.2.1. Primary Endpoint**

The primary endpoint of the OLE is the safety of long-term treatment of losmapimod based on AEs, clinical laboratory tests, ECGs, vital signs, and physical examination, based on protocol versions 4.0 and 5.0.

### **3.2.2. Secondary Endpoints**

The secondary endpoints of the OLE are as follows:

- Changes from baseline in MFF, LMV, and MFI after long-term dosing (at every 12-week time point), based on protocol version 4.0
- Plasma concentrations of losmapimod after long-term dosing (at every 12-week time point), based on protocol versions 4.0 and 5.0

### **3.2.3. Exploratory Endpoints**

The exploratory endpoints of the OLE, based on protocol version 4.0, are as follows:

- Changes from baseline in COAs after long-term dosing (at every 12-week time point):
  - RWS with and without weights
  - Classic and FSHD TUG
  - Muscle strength by hand-held quantitative dynamometry
  - MFM Domain I
  - FSHD-HI
  - PGIC
- Changes from baseline in inflammatory, immune, apoptotic, and other muscle disease transcripts in circulating proteins in plasma and serum after long-term dosing (at every 24-week time point)

### **3.3. Treatments**

During the OLE, all subjects will receive 15 mg losmapimod BID open-label.

## 4. General Statistical Considerations

The following conventions will be used for all data presentations and analyses unless otherwise specified.

Appropriate descriptive statistics will be computed and displayed for both continuous and categorical variables. For continuous and quantitative variables, summaries will include n (number of subjects with non-missing data), mean, standard deviation (SD), standard error (SE), Q1 (first quartile), Q3 (third quartile), median, minimum, and maximum. Reporting conventions for descriptive statistics will follow the [REDACTED] Standard TLF Guidelines. For categorical variables, summaries will include the number and percentage of subjects who are in a particular category. Percentages will be computed based on the number of non-missing data points for patients in the applicable analysis set. Reporting of percentages will follow the [REDACTED] Standard TLF Guidelines.

A total column will be presented for demographics, baseline characteristics, protocol deviation and concomitant medication summaries.

All data will be listed by treatment sequence, subject ID, age, sex, race, analysis period, and visit date, if available. Data from both the placebo-controlled treatment period and OLE will all be included in a listing. Any repeat assessments or additional assessments, along with any unscheduled visits, will be presented in the listings. Sort order of data listings will be treatment sequence, subject ID, analysis period, and visit date, if available.

Statistical tests will be 2-sided, unless otherwise specified. P-values will be reported to 4 decimal places, with p-values less than 0.0001 reported as “<0.0001”.

All analyses will be performed using Statistical Analysis Software (SAS®, release 9.4 or higher). A separate document as an appendix to this SAP will contain the tables, listings, and figures (shells).

### 4.1. Analysis Periods

For the purposes of efficacy and safety data analysis, and for reporting, two analysis periods for post baseline data are defined: placebo-controlled treatment period and OLE. The placebo-controlled treatment period encompasses data through Week 48 or Week 24 for subjects who prior to the COVID-19 pandemic had the option to roll over into the OLE at Week 24. The OLE encompasses all losmapimod data starting a day after the Week 48 visit or Week 24 visit for subjects who prior to the COVID-19 pandemic had the option to roll over into the OLE at Week 24. The duration of OLE is defined for each subject as the time after completion of the Week 48 or Week 24 for subjects who prior to the COVID-19

pandemic had the option to roll over into the OLE at Week 24 through completion of the safety follow-up after the end of treatment or discontinuation of the study.

In addition, a supplementary analysis period will be considered which is the losmapimod exposure period that encompasses all losmapimod exposure data, irrespective of when the losmapimod exposure starts (i.e., baseline or OLE).

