#### **4.4. Baseline, Study Day, and Change from Baseline Definitions**

Unless indicated otherwise, baseline will be defined as the last non-missing evaluation on or before the day of first dose of study drug in the placebo-controlled treatment period. If the last non-missing evaluation and the study drug administration occur on the same day, timing of the evaluation will be used to determine the pre- or post-dose. If timing is not available, the evaluation is considered pre- or post-dose based on the schedule of events for that assessment. For example, AEs and concomitant medication are considered post-baseline evaluations.

For the OLE baseline, it is defined as the last non-missing evaluation before the first dose of losmapimod in the OLE.

Relative study days will be calculated as:

$(\text{assessment date} - \text{first study drug administration date}) + 1$

if the assessment date is on the same day or after the first dosing date, otherwise:

$(\text{assessment date} - \text{first study drug administration date})$ .

Where applicable, study day relative to first dose of losmapimod will also be provided and this will be calculated as:

$(\text{assessment date} - \text{first losmapimod administration date}) + 1$

if the assessment date is on the same day or after the first dosing date, otherwise:

$(\text{assessment date} - \text{first losmapimod administration date})$ .

Both study days will be presented on all listings where appropriate.

Change from baseline will be computed as (post-baseline assessment value - baseline assessment value). Percent change from baseline will be computed as  $(\text{change from baseline value} / \text{baseline assessment value}) * 100$ . For the OLE visits, change from baseline will be computed based on both baseline assessment value, baseline in the placebo-controlled treatment period and baseline in OLE.

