Data while the subject is on losmapimod will be considered in the analysis. For subjects who were randomized to losmapimod at baseline, data from both the placebo-controlled treatment period and OLE will be included in the analysis. For subjects who were randomized to placebo and transitioned to losmapimod at OLE, their data under losmapimod are considered in the analysis. A linear mixed-effects model will be used to analyze the longitudinal composite scores for each treatment sequence, with intercept and time as random effects, and with adjustment for repeat number category and region (EU, USA, and Canada). An unstructured covariance matrix will be used to model the correlations between repeated measurements within each subject. In addition, the % change/year will be presented and will be derived as  $[(\text{slope}/\text{baseline}) * (365/T) * 100]$  where baseline is the LS mean of the intercept and T is the duration of treatment with losmapimod minus 1.

- (2) % change/year for the losmapimod group and placebo group using data from the placebo-controlled treatment period for subjects who completed 48 weeks of treatment in the placebo-controlled treatment period

A linear mixed-effects model will be used to analyze the longitudinal composite scores, with treatment sequence as a fixed effect, and intercept, time and treatment sequence-by-time interaction as random effects, adjusting for repeat number category and region (EU, USA, and Canada). An unstructured covariance matrix will be used to model the correlations between repeated measurements within each subject. Within-treatment sequence LS mean of slope and the associated SE, intercept and the associated SE, difference in the LS mean of slope and the associated 2-sided 95% CI and 2-sided p-value will be derived from the linear mixed-effects model and will be provided in the summary table. In addition, the % change/year will be presented. It will be derived as  $[(\text{slope}/\text{baseline}) * (365/T) * 100]$  where baseline is the LS mean of the intercept and T is the duration of treatment with study drug minus 1. Difference in % change/year between treatment sequences will also be presented.

- (3) % change/year for each treatment sequence using data from the OLE for subjects who completed 48 weeks of treatment in the placebo-controlled treatment period

The same approach as in (2) will be used to analyze the longitudinal composite scores in the OLE.

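### As worded, the OLE slopes, and the on-losmapimod slope of subjects who switch from placebo at Week 48, leave out the Week 48 assessment and lose MRI slope precision

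*SAP*

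**What the plan says.** SAP 4.1 divides the data in two: "two analysis periods for post baseline data are defined: placebo-controlled treatment period and OLE". The boundary is explicit on both sides. "The placebo-controlled treatment period encompasses data through Week 48 or Week 24" (the latter for the early rollovers), and "The OLE encompasses all losmapimod data starting a day after the Week 48 visit". SAP 3.1 agrees: "The first dose of OLE drug will be the day after the Week 48 visit". For a subject randomised to placebo, the Week 48 assessment therefore comes before any losmapimod.

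SAP 8.1 defines three annualised slopes. Slope (3) is the percentage "change/year for each treatment sequence using data from the OLE for subjects who completed 48 weeks of treatment". Slope (1) uses on-losmapimod data: "For subjects who were randomized to placebo and transitioned to losmapimod at OLE, their data under losmapimod are considered in the analysis". Both come from mixed models with random intercept and time, and the LS mean of the intercept serves as the baseline in the % change/year formula.

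SAP 4.4 adds: "For the OLE baseline, it is defined as the last non-missing evaluation before the first dose of losmapimod in the OLE". For a subject who switches at Week 48 that is normally the Week 48 value. Its stated use is change scores: "For the OLE visits, change from baseline will be computed based on both baseline assessment value", meaning the study baseline and the OLE baseline. SAP 8.1 does not say whether this record enters a slope model.

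**The concern.** SAP 8.1 says slopes (2) and (3) are there to explore whether early treatment beats delayed treatment and whether progression in the placebo group slows once losmapimod starts. A slope after the switch is best anchored at the switch. Without Week 48:

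- The first MRI in the slope is Week 72, so change over the first 24 weeks of open-label drug does not inform it.
- A subject whose only OLE scan is Week 72 gives no within-subject slope.
- If time zero is the switch, the intercept that forms the % change/year denominator is extrapolated 24 weeks back from the first scan used.
- The slope is less precise.

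Two programmers could also read the text differently and produce different slopes from the same data.

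**Working it through.** The documents state no precision or power for the OLE slopes, so there is no figure of the plan's to reproduce.

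**Inputs**
- MRI before the switch: screening, Week 12, Week 48 (Protocol 3.1.1).
- MRI in the OLE: Weeks 72, 96, 120, 144 and so on (SAP Appendix 14.2). RWS, TUG and dynamometry: every 12 weeks from Week 60.
- Likely last scan: efficacy collection ends when protocol version 5.0 is executed (SAP 3.1). That version is dated 16 August 2022, and enrolment was complete by 10 April 2020 (Protocol 3.1.1). The interval is 858 days, and 858/7 = 122.6 weeks. Entry in mid-October 2019 (assumed to be the earliest entry that missed the Week 24 rollover) gives about 148 weeks. The last scan is therefore likely Week 120 or 144, or later if sites adopted version 5.0 later.
- Not given: residual SD σ and between-subject SD of the yearly slope τ. Let r = τ/σ; r = 0 and r = 1 are shown.

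**Formula.** With complete visits and a random intercept and slope, the per-subject variance of the mean slope is τ² + σ²/Sxx, where Sxx is the sum of squared deviations of the visit times. In units of σ², V = r² + 1/Sxx. Loss of precision = 1 − V(with Week 48)/V(without).

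**Sxx for MRI**
- Last scan Week 120, without Week 48: 24² + 0 + 24² = 1152 weeks². With it: 36² + 12² + 12² + 36² = 2880. Ratio 2.5.
- Last scan Week 144, without: 2880. With: 48² + 24² + 0 + 24² + 48² = 5760. Ratio 2.0.
- In years² (divide by 52.1786² = 2722.6): 1152 → 0.423, 2880 → 1.058, 5760 → 2.116.

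**Loss for MRI**

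| Last scan | r | V without | V with | Loss | SE inflation |
|---|---|---|---|---|---|
| Week 120 | 0 | 2.363 | 0.945 | 60% | 1.58 |
| Week 144 | 0 | 0.945 | 0.473 | 50% | 1.41 |
| Week 120 | 1 | 3.363 | 1.945 | 42% | 1.31 |
| Week 144 | 1 | 1.945 | 1.473 | 24% | 1.15 |

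**12-weekly endpoints, r = 0.** To Week 120, Sxx goes from 2520 to 4032 weeks² (ratio 1.6, loss 38%). To Week 144 it goes from 6048 to 8640 (ratio 1.43, loss 30%).

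**Contrast of pre- and post-switch slopes fitted separately, r = 0.** Take the earlier scans as Weeks 0, 12 and 48 (mean 20, Sxx = 400 + 64 + 784 = 1248). If Week 48 is in both slopes, their errors share it. In units of σ² per week², with the last scan at Week 120:
- Covariance = (28/1248) × (−36/2880) = −0.000280.
- Variance of the difference with Week 48 = 1/1248 + 1/2880 + 2 × 0.000280 = 0.00171.
- Without it = 1/1248 + 1/1152 = 0.00167. Ratio 1.02.

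With the last scan at Week 144, the covariance is (28/1248) × (−48/5760) = −0.000187, the variances are 0.00135 and 0.00115, and the ratio is 1.17.

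**The case against.** The strongest reply is that the plan never expressly removes Week 48. SAP 4.1 defines its periods for post-baseline data, SAP 4.4 makes the last pre-OLE value the OLE baseline, and SAP 8.1 calls the intercept a baseline and gives slope (3) the same approach as slope (2). Applied with full strictness, 4.1 would also take the study baseline out of slope (2), which is hardly intended. This stands in part: the exclusion is the literal reading, not an express instruction. It does not resolve the gap, because no text brings the OLE baseline into a slope model. For slope (1), the limit to data under losmapimod shuts out a pre-dose record without help from 4.1.

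Leaving an off-drug record out of an on-drug slope can also be defended. Protocol 3.2.2 expects MRI changes to take longer to detect than changes in DUX4 expression, and an anchor at Week 48 assumes a linear course from the first dose. That supports a sensitivity analysis.

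Two further limits apply. SAP 8.1 does not define the time origin, so the 24-week extrapolation is conditional on time zero being the switch. The text available for this review also breaks off before the longitudinal part of Appendix 14.1, so the exact form of the modelled composite could not be checked.

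A reader might infer that the MRI slopes always lose half or more of their precision. They do not: that needs a last scan by Week 144 and, at Week 144, no between-subject slope variance, whereas SAP 8.1 specifies a random slope. A reader might also infer that adding Week 48 sharpens the before-and-after comparison within the placebo group. For separately fitted slopes it does not when the last scan is Week 120 or later.

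**Conclusion.** The concern holds as a gap in specification with a real cost. Read literally, Week 48 is left out of slope (3) and out of slope (1) for former placebo subjects who switch at Week 48. At the likely follow-up the MRI slopes lose between 24% and 60% of their precision over r = 0 to 1. The result assumes complete 24-weekly scans and a last scan at Week 120 or 144; r is an assumption. RWS, TUG and dynamometry lose less.

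Slope (1) for subjects on losmapimod throughout keeps Week 48, and change from OLE baseline already uses it. Restoring the anchor helps the individual slopes and the between-sequence difference in the OLE.

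**What to change.** In SAP 8.1, define the time origin and state that:

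- slope (1) includes, as time zero, the last assessment before the first losmapimod dose (study baseline for subjects randomised to losmapimod, OLE baseline for those randomised to placebo);
- slope (3) includes, as time zero, the OLE baseline of SAP 4.4;
- each slope is also reported without the anchor as a sensitivity analysis, because the anchor assumes linearity from the first dose.

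SAP 8.2.1 to 8.2.3 follow the methods of 8.1, so RWS, TUG and dynamometry inherit the change. If the Week 48 scan is missing, the 4.4 rule falls back to an earlier one; the text should say that such a record keeps its actual date.

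The cost is SAP wording and one extra model run per endpoint. No new data are needed, because the Week 48 assessments are already scheduled and required for rollover at that visit.

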^b If a subject prematurely discontinues study treatment during the placebo-controlled treatment period, they will be encouraged to remain in the study and continue with all other aspects of the study. If a subject decides to prematurely discontinue study treatment during the placebo-controlled treatment period and not continue with all other aspects of the study, they will be considered to have withdrawn from the study. If a subject withdraws from the study during the placebo-controlled treatment period, they will be asked to complete an ET visit as soon as possible after the decision to terminate study participation and to complete the safety follow-up visit 7 (±3) days after their last dose of study drug. If the ET visit will be scheduled more than 7 days after the last dose of study drug, the safety follow-up and ET visits may be combined, with no duplication of assessments required.

^c The safety follow-up visit 7 (±3) days after the last dose of study drug should only be completed by subjects who are not rolling over into the OLE.

^d Scheduled visits may be split over 2 days if required, with a maximum of 5 business days in between visits. Unscheduled visits may be performed if clinically indicated. Subjects can travel for MRI or muscle biopsy if needed, but the use of a study-approved MRI scanner should be consistent during the trial.

^e Weight and height will be measured with shoes off and preferably with the same balance at each visit. Body mass index will be calculated at Screening.

^f Medical history will be reviewed at baseline to ensure no changes have occurred since the screening visit.

^g FSHD-specific history will be recorded at screening or at a subject's next scheduled study visit, if not previously recorded.

^h Urine drug screen for drugs of abuse including cocaine, amphetamines, opiates (morphine), benzodiazepines, and cannabinoids.

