^t The choice of the muscle(s) to be biopsied in this study will be determined by the investigator, informed by skeletal muscle MRI during screening. The bilateral vastus lateralis, vastus medialis, lateral gastrocnemius, medial gastrocnemius, and tibialis anterior will be evaluated for eligibility by MRI using a central reader. Only those muscles that are STIR positive with the predetermined range of muscle fat fraction will be eligible for biopsy. The 12 patients who rolled over at Week 24 will not undergo the Week 36 muscle biopsy.

^u Blood samples for PK will be collected at Day 1 (baseline), Week 4, Week 16, and Week 36 at the following time points: immediately predose and 4 hours (\pm 30 minutes) after administration of the study dose. Blood samples will also be taken, when feasible, after dosing during the Week 12, Week 24, and Week 48 visits, preferably \geq 1 hour after dosing.

^v Blood samples for target engagement will be collected on Day 1 (baseline), and Week 16 or Week 36, at the following time points: immediately predose and 4 hours (\pm 30 minutes) after administration of the study dose.

^x The appropriate amount of study drug supply (losmapimod or placebo) will be given to the subject at each applicable visit to allow for dosing until their next scheduled study visit plus additional tablets to cover the visit window. Study drug (losmapimod or placebo) will be administered as 2 tablets taken twice daily and should be taken with food. Subject diaries may only be used for a portion of the placebo-controlled portion of the trial to record the date and time of each dose taken. This information may also be used to calculate compliance. Subjects will record the date and time of each dose of study drug taken (losmapimod or placebo) in the subject diary. Subjects may be provided additional study drug via courier service, as applicable.

^y Subjects who are rolling over into the OLE will be dispensed open-label losmapimod at the time of the rollover visit. Subjects may be provided open-label losmapimod via courier or shipping service, as applicable.

^z All medications taken within 28 days before screening through the safety follow-up visit will be recorded.

^{aa} Large window given to accommodate the COVID-19 pandemic.

^{bb} It is optional to perform coagulation studies prior to muscle biopsies. Refer to your institutional guidelines.

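### The OLE analysis period starts the day after the rollover visit rather than at the first open-label dose, so adverse events around a late or same-day start are misplaced

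*SAP*

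**What the plan says.** SAP 4.1 fixes the OLE start by visit: "The OLE encompasses all losmapimod data starting a day after the Week 48 visit or Week 24 visit", the Week 24 date being for the early rollovers. The other period ends at the visit: "The placebo-controlled treatment period encompasses data through Week 48 or Week 24 for subjects who prior to the COVID-19 pandemic" could roll over at Week 24.

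SAP 3.1 supplies the link to dosing. For Week 48 rollovers, "The first dose of OLE drug will be the day after the Week 48 visit". For the earlier group, "The first dose of OLE drug for these subjects will be the day after the Week 24 visit".

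SAP 4.4 uses a different anchor for the OLE baseline: "it is defined as the last non-missing evaluation before the first dose of losmapimod in the OLE". SAP 7.2.1 likewise measures exposure from the date of the first losmapimod dose.

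The protocol names no day for the first open-label dose. Footnote y to Table 2 gives the default, "Subjects who are rolling over into the OLE will be dispensed open-label losmapimod at the time of the rollover visit", and then adds: "Subjects may be provided open-label losmapimod via courier or shipping service, as applicable". No limit on shipping time is stated. Footnote d adds: "Scheduled visits may be split over 2 days if required, with a maximum of 5 business days in between visits".

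**The concern.** Safety and tolerability are the primary objective of the OLE. For subjects first randomized to placebo, rollover is the one planned change of drug, and the weeks just after it are where an early drug effect would show. An event that precedes the first open-label dose says nothing about losmapimod in such a subject.

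The SAP's boundary is correct only if dosing starts exactly one day after the visit. Sections 3.1 and 4.1 give no rule for a subject who starts on another day, and they do not say which date of a split visit counts. Protocol 3.2.2 itself describes drug delivery at clinic visits as compromised by the pandemic, with a risk of treatment gaps, so a delayed start is not far-fetched.

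**Working it through.** The plan states no gap length and no count of misplaced events, so there is no figure to reproduce. The check is one of date logic, followed by an illustration of size.

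**Date logic.** Let V be the date of the rollover visit and D the date of the first open-label dose. The OLE period starts at V + 1, so the misplaced time is k = D − (V + 1) days.

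- D = V + 1, as SAP 3.1 expects: k = 0 and nothing is misplaced.
- D later than V + 1: k days lie after the end of the placebo-controlled period and before any open-label losmapimod. By calendar date they are in the OLE. If the restriction to losmapimod data in SAP 4.1 is applied literally, a former-placebo subject's events on those days are in neither period.
- D = V: events after the dose on the visit day stay in the placebo-controlled period, although the subject has taken open-label drug.

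**Does another rule catch the gap events?**

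- SAP 9.1 defines treatment-emergent events from the first dose of study drug. SAP 1 defines study drug to include placebo. A gap event in a former-placebo subject is therefore treatment-emergent.
- SAP 9.1 then presents these events separately by analysis period. No step removes an event that precedes the first open-label dose.
- SAP 4.1 also defines a losmapimod exposure period tied to actual dosing. In the list of planned tables (SAP 14.4), only the duration and compliance tables, 14.1.6.1 and 14.1.6.2, use it. No adverse event table does.

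**Illustrative size.**

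- Former-placebo subjects: 80 enrolled (SAP 4.8), allocated 1:1 (Protocol 5.1), so 80/2 = 40. This assumes an even split and that all roll over.
- Gap: k = 7 days in every subject. This is an assumption. It equals 5 business days in calendar time and is not an estimate of shipping time.
- Person-days: 40 × 7 = 280.
- Share of the first 12 OLE weeks: 7/84 = 8.3%.
- Share of Week 48 to 216: 168 weeks × 7 = 1,176 days, and 7/1,176 = 0.6%.

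For a rough event count, Protocol 1.4 reports adverse events in 406/735 (55%) of placebo patients in earlier repeat-dose studies, none in FSHD. Taking 24 weeks (168 days) as their length, which Protocol 1.5 gives for the majority of losmapimod studies, the daily rate is r = −ln(1 − 406/735)/168 = 0.00478. Expected former-placebo subjects with a gap event are 40 × (1 − exp(−7r)) = 1.3. At k = 1 the figure is 0.2, and at k = 0 it is 0.

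**The case against.** The best defence is that the plan is consistent when followed. SAP 3.1 puts the first dose on the day the period begins, so the gap is zero. Protocol 4.2 also defines the OLE as the time after completion of the Week 48 visit, and SAP 4.1 repeats that for the duration of the OLE. A reader might infer that the two documents contradict each other on switch timing. They do not: the protocol is silent on the first-dose day, and the SAP fills the silence.

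Courier supply is also not the default. Table 2 schedules dispensing at Week 48, footnote y is printed against the Week 24 dispensing mark (though its wording covers any rollover visit), and elsewhere the protocol mentions couriers mainly for additional drug. A split visit might seem to create a gap by itself. It does so only if its first date is taken as the visit date, and both documents speak of completion.

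The reach is limited too. Summaries are descriptive. Cumulative adverse event tables through the data cut do not depend on the boundary. Laboratory, vital sign and ECG summaries run across both periods. The OLE baseline would normally be the rollover-visit value under either anchor. SAP 4.4 adds study day relative to first losmapimod dose to listings where appropriate, so a gap event could be recognized there.

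All of this stands, and it makes the point small. It does not supply a rule for a subject who starts on another day. SAP 3.1 states an expectation, and a listing does not correct a table.

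**Conclusion.** The gap in the rules is real and minor. The OLE period depends on the visit while OLE baseline and exposure depend on dosing, and no adverse event rule or table handles a first open-label dose on any day other than the one after the visit.

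The size runs from zero, if SAP 3.1 was met in every subject, to the illustrative ceiling above. That ceiling assumes all 40 former-placebo subjects roll over with the same 7-day gap. The event count also borrows a rate from non-FSHD studies. Any effect is concentrated in the first 12 OLE weeks and is under 1% of follow-up to Week 216.

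Two stronger readings are not supported. A reader might infer that placebo-time events will be counted as losmapimod events. The wording of SAP 4.1 also allows them to fall in neither period, and the subject may have been off drug in the gap. Nor can longer courier delays be assumed: the documents give no shipping time, so a figure such as 14 days would have no source.

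**What to change.** In SAP 4.1, start the OLE period for each subject at the recorded date, and time if available, of the first open-label losmapimod dose. Use the day after completion of the rollover visit (its last date if split) only when the dose date is missing.

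Keep former-placebo events between the rollover visit and that dose out of the OLE losmapimod adverse event tables. Show them in a small separate display as events before the first open-label dose. Do not move them into the placebo-controlled period. That period has its own SAP and database lock, and late additions could make the OLE report disagree with locked results. They would also label possibly untreated days as placebo-controlled time.

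Reconcile the switch-timing text in SAP 3.1 and 4.1 with the protocol's dispensing text. This concerns the analysis anchor only and takes no position on when drug should be dispensed or taken.

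The cost is a few sentences, one extra small display and minor programming. The first-dose date is already needed for OLE baseline and, in former-placebo subjects, for exposure.
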